### 1.1 Primary Objective

*To evaluate feasibility and efficacy of photobiomodulation therapy (PBM) in reducing oral mucositis in children and adolescents at risk for grade 3 oral mucositis undergoing an allogeneic hematopoietic cell transplant (HCT).*

Hypothesis 1: Children and adolescents will receive 75% of the attempted PMB treatment and will be less likely to develop grade 3 oral mucositis from the 1st day of conditioning to day +20 transplant or engraftment (event occurring first)

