## 4. DESIGN AND METHODS

### 4.1 Design and Study Overview

This study will enroll children and adolescents prior to admission for an allogeneic HCT, and those undergoing an autologous transplant at deemed at risk for grade 3 oral mucositis. Light therapy will be administered by trained persons within Nursing Research Division: [name], [name], [name] and [name]. The parent may hold the device in place with assistance from the trained persons. Patients will receive extra-oral and intra-oral PBM on the first day of conditioning, those undergoing an allogeneic HCT will have treatment daily until engraftment or +Day 20 (event occurring first). For those undergoing an autologous transplant treatment will continue until engraftment or until the patient is without mucositis for two consecutive days. If the patient becomes acutely ill during therapy and misses 4 consecutive days of PBM, the data will not be evaluated. These patients will be replaced to give 66 evaluable patients for the primary objective. Patients in isolation will continue to receive PBM with the device covered in plastic and cleaned prior to leaving the isolation holding area.

The PBM will be delivered through application of the LED Cluster Probe externally to the right external buccal, left external buccal, mid face with mouth open and submandibular and left/right cervical. Patients who develop an oral lesion, intra-oral directed therapy will be administered with the dental light probe. For patients that can tolerate, an intraoral probe will deliver light directly onto the oral mucosa, this will then replace the mid face application with mouth open. Each laser application will be timed at 60 seconds. [8] The PBM treatment will be administered via the THOR Model LX2M unit. All participants will receive the standard mouth care regimen prescribed for HCT patients. Observation and treatment will begin the first day of conditioning and continue daily until engraftment (2 consecutive days of ANC  $\geq$  500) or Day +20 (which comes first) and until mucositis resolution for two consecutive days for the autologous transplant.

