Feasibility will be assessed similar to Treister et al [20] through the number of successful treatments administered by the total number of attempted treatments, providing the percentage of successful treatment administered. Daily treatment will include 6 sites of PBM application, with application documented as receiving all 6 applications, in part treatment (at least one to five sites) or no treatment. A successful treatment is defined as the treatment is successfully administered to 4 or more sites. Reasons for partial or no treatment will be documented. Criteria for feasibility is that the percentage of successful treatments administered exceeds 75%. The collected data will be summarized for total days on protocol, days treatment is received, cumulative dose and the number of treatments received at each site.

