**Table Summary of Photobiomodulation Therapy Delivered**

Case number	Days on protocol a	Days received treatment b	Total cumulative dose c (J/cm  )	Treatment site = right face	Treatment site = midline face	Treatment site = left face	Treatment site = left neck	Treatment site = midline neck	Treatment site = right neck

aDays on protocol defined as from the first day of hematopoietic cell transplantation conditioning through engraftment

bDays received treatment defined as days with treatment during any of the on-protocol days

cCummulative dose define as single treatment dose multiplied by the number of treatment sites (up to 6 in total) for each treatment session

Efficacy will be assessed with assessment of grade 3 mucositis development from day 1 of conditioning to Day +20 of transplant or engraftment as a binary outcome (yes/no)

[figure not shown]
Daily observation: The observation of oral mucositis will be conducted by non-study staff and conducted as clinical care by the nurse, advanced practice provider and/or physician.

Assessment: Each patient or parent proxy will complete the Children's Mucositis Assessment via ipad along with documentation of mucositis grade, duration, days of nutrition support, use of narcotics, positive oral and blood cultures.

Each patient will be matched and compared to a previously treated patient. The comparison will be matched on primary disease, conditioning regimen, age and sex, with comparison of treatment variables of mucositis grade, duration, pain medications, days of nutritional support, blood and oral cultures, to day +20 or engraftment (depending upon which occurs first).

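### The 75% feasibility criterion is stated over attempted treatments, a term the plan leaves undefined; read literally, it can be met while many scheduled PBM sessions are missed

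*Combined protocol and SAP*

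**What the plan says.** Section 4.1 (Design and Study Overview) defines the feasibility percentage by dividing "the number of successful treatments administered by the total number of attempted treatments". The decision rule follows: "Criteria for feasibility is that the percentage of successful treatments administered exceeds 75" percent. Hypothesis 1 uses the same basis in Section 1.1 and again in Section 10.2.1: "Children and adolescents will receive 75% of the attempted PMB treatment". No section defines an attempt.

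The same paragraph of Section 4.1 sets the unit of success: "A successful treatment is defined as the treatment is successfully administered to 4 or more sites". It has each day's "application documented as receiving all 6 applications, in part treatment (at least one to five sites) or no treatment", and adds: "Reasons for partial or no treatment will be documented". It does not say whether a no-treatment day is a failed attempt or no attempt.

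PBM is scheduled every day from the start of conditioning; for allogeneic patients it ends at engraftment or Day +20, whichever is earlier. Section 4.1 also provides that an acutely ill patient who misses four days in a row is not evaluated and is replaced, to reach 66 evaluable patients for the primary objective. Section 7.1 has a matching off-study criterion (more than three consecutive days).

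Days on protocol and days treated are summarised (Sections 4.1, 6.2 and 10.2.1) and tabulated per case, with no threshold attached. Footnote a of the table in Section 4.1 runs days on protocol "from the first day of hematopoietic cell transplantation conditioning through engraftment", with no Day +20 limit.

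**The concern.** Section 1.0 gives the goal as bringing PBM into routine daily nursing care, and the pediatric evidence in Section 2.2 reports that a guideline recommendation was weak partly because feasibility in routine care was unknown. The relevant quantity is therefore how many of the planned daily sessions are delivered. Success per attempt answers a narrower question: once staff start a session, do they reach at least four of the six sites?

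The two differ by the share of scheduled days on which a session is attempted. If unattempted days are left out, that share has no influence on the verdict, and PBM could be declared feasible with substantial under-delivery. If no-treatment days are counted as failed attempts, the same data could give the opposite verdict. A primary criterion should not depend on a choice between two readings made at analysis.

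The replacement rule raises a related problem. Missing four days in a row is itself information about feasibility, yet those patients leave the set on which feasibility would be judged.

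**Working it through.** **Plan's own figure.** The 75% threshold is set by definition. The documents give no calculation behind it, so there is nothing to reproduce.

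**Identity.** For one patient, or for totals over patients:

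successful / scheduled = (successful / attempted) × (attempted / scheduled), or D = S × A.

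The plan's literal rule is S > 0.75. A does not appear in it.

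**Break-even.** D is 0.75 or less when A ≤ 0.75 / S. The values of S are illustrative.

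| Success per attempt, S | Delivery is 75% or less when attempted share is at or below | Unattempted share at that point |
|---|---|---|
| 80% | 0.75 / 0.80 = 93.75% | 6.25% |
| 90% | 0.75 / 0.90 = 83.3% | 16.7% |
| 95% | 0.75 / 0.95 = 78.9% | 21.1% |
| 100% | 0.75 / 1.00 = 75% | 25% |

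**Delivery with S fixed at 80%**, which passes the literal rule throughout. The values of A are assumptions.

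- 90% attempted: 0.80 × 0.90 = 72% of scheduled sessions
- 75% attempted: 0.80 × 0.75 = 60%
- 50% attempted: 0.80 × 0.50 = 40%

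**One data set, two verdicts.** Assume 28 scheduled days, 20 attempted and 16 successful. If unattempted days are left out, the score is 16/20 = 80% and passes. If every scheduled day counts, it is 16/28 = 57% and fails.

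**What the missed-days rule limits.** A patient stays evaluable if no four consecutive days are missed, so at least floor(days / 4) of the scheduled days must be treated. For 28 days that is 7, leaving 21 missed. Such a patient could score 7/7 = 100% per attempt with 7/28 = 25% of sessions delivered. Over an assumed 21 to 30 scheduled days, the largest missed share compatible with staying evaluable is about 75% to 78% (18/24 = 75%; 21/27 = 78%). This is a bound, not a forecast.

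**Footnote a, checked separately.** Section 4.1 ends allogeneic treatment at the earlier of engraftment or Day +20. Section 6.3 takes patients off study on the last day of PBM. Footnote a counts to engraftment alone. For an allogeneic patient who engrafts after Day +20, footnote a would include days on which Section 4.1 schedules no PBM.

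**The case against.** The strongest reply is that the plan may already count missed days. The no-treatment category and its documented reasons stand in the feasibility paragraph itself, and a zero-site category there fits a reading in which such days are failed attempts. On that reading the gap closes. This stands as a possibility: a reader might infer that untreated days certainly drop out, and the documents do not establish that. They do not establish the opposite either, and the ratio and both statements of Hypothesis 1 refer to attempts.

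Second, Section 4.1 says feasibility is assessed in a similar way to a cited feasibility study, which may define an attempt, and delivery per attempt is a legitimate measure. That study's definition cannot be checked from the documents, and the term still needs defining here.

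Third, missed days are not hidden, because days on protocol and days treated are listed per case. That is correct, but neither figure enters the pass/fail rule.

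Fourth, the unattempted rates are assumed and the 7-of-28 case is extreme. Both points are fair. The plan also gives no support for calling illness, refusal or staffing the main barrier to delivery, and the point does not need it.

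A reader might also take footnote a as a further source of optimism. It is not: days on protocol is the denominator of no criterion, and if someone divided by it, extra days would make delivery look worse. The ranges in Section 2.2 (onset as early as Day -3, up to 26 days from onset to engraftment) imply at least one engraftment on Day +23 or later (-3 + 26 = 23), but the transplant type of that patient is unclear, so they do not show that footnote a overcounts an allogeneic patient.

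**Conclusion.** The point holds in this form: the primary feasibility criterion rests on an undefined denominator and, read literally, can be met while many scheduled sessions are missed. The identity and break-even values are exact. How far the percentage would move depends on attempt rates and numbers of treatment days that the documents do not give, so the examples show sensitivity, not expected bias. At 80% success per attempt, 6.25% of scheduled days unattempted is enough to change the verdict; at 100% it takes 25%.

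The replacement rule takes the courses with the longest gaps out of the assessment. Its effect cannot be sized, because no frequency is given. A reader might infer that the feasibility result will be too favourable; the documents support only that it could be, and that the plan does not prevent it. The footnote mismatch is a minor, separate inconsistency.

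**What to change.** In Sections 1.1, 4.1 and 10.2.1, judge the 75% criterion on all scheduled PBM days for every patient who starts PBM, including those later taken off study or replaced. Count a day as successful if at least four sites are treated, as now, and count no-treatment days as not successful. State in advance how scheduled days after removal, withdrawal or death are counted. Report success per attempt as a secondary figure, with a definition of an attempt, and show attempted over scheduled days beside it.

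Separately, reconcile footnote a with the treatment window in Sections 4.1 and 6.3, so that days on protocol and scheduled days cover the same period. Which window applies is for the sponsor to settle.

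The cost is small but not nil. Treated, partial and untreated days and the reasons are already recorded, and time to engraftment is abstracted from the chart; the sponsor should confirm that these are also available for patients taken off study. The criterion becomes stricter than the per-attempt version and the reported percentage may be less favourable. If the sponsor prefers to keep 75% on the per-attempt basis, the plan should say so and limit the feasibility conclusion to delivery once a session is started.

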**Table Summary of Photobiomodulation Therapy Delivered**

Case number	Days on protocol a	Days received treatment b	Total cumulative dose c (J/cm  )	Treatment site = right face	Treatment site = midline face	Treatment site = left face	Treatment site = left neck	Treatment site = midline neck	Treatment site = right neck

aDays on protocol defined as from the first day of hematopoietic cell transplantation conditioning through engraftment

bDays received treatment defined as days with treatment during any of the on-protocol days

cCummulative dose define as single treatment dose multiplied by the number of treatment sites (up to 6 in total) for each treatment session

Efficacy will be assessed with assessment of grade 3 mucositis development from day 1 of conditioning to Day +20 of transplant or engraftment as a binary outcome (yes/no)

[figure not shown]
Daily observation: The observation of oral mucositis will be conducted by non-study staff and conducted as clinical care by the nurse, advanced practice provider and/or physician.

Assessment: Each patient or parent proxy will complete the Children's Mucositis Assessment via ipad along with documentation of mucositis grade, duration, days of nutrition support, use of narcotics, positive oral and blood cultures.

Each patient will be matched and compared to a previously treated patient. The comparison will be matched on primary disease, conditioning regimen, age and sex, with comparison of treatment variables of mucositis grade, duration, pain medications, days of nutritional support, blood and oral cultures, to day +20 or engraftment (depending upon which occurs first).

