**Intervention:** PBM is defined as the application of coherent or non-coherent light to an area of pathology to promote tissue regeneration, reduce inflammation, and relieve pain. The biological mechanism of PBM allows intracellular absorption of energy by intracellular organelles and molecules; however, the amount and specifics of energy absorption is dependent upon the wavelength and rate of energy delivery dependent on the power of the device. PBM is FDA approved for tissue damage, pain and inflammation. There is no age limitation.

**Brief Outline of Treatment Plan:** Children, adolescents and young adults admitted for an allogeneic HCT and those determined by the transplant team to be at risk for  $\geq$  grade 3 oral mucositis will be eligible to receive PBM (34 x 660 nm 10 mW, 35 x 850 nm 30 mW; 1390 mW total power output at an irradiance of 50mW/cm^2). The PBM will be administered by trained research staff beginning on the first morning of the conditioning regimen (plus/minus 2 days) and continue daily until Day +20 or engraftment (event occurring first) and for allogeneic continue daily until engraftment or until the patient is

Protocol MNEMONIC and Title: Prevention/Treatment of Oral Mucositis in Children and Adolescents undergoing Hematopoietic Cell Transplant (HCT) using Photobiomodulation Therapy (PBM)
without grade 1 (no) mucositis for two consecutive days. All patients will receive the standard mouth care regimen prescribed for transplant patients. The nurse, advance nurse practitioner and physician caring for the patient will grade mucositis daily per the Common Toxicity Criteria (version5), and pain will be documented per institutional pain assessment scale (0-10). Patient- reported pain, and oral function will be collected daily.
Study Design: This two-stage design study will assess for development of grade 3 mucositis during daily PBM treatment.
Sample Size: 66
Data Management: Data management and statistical analysis will be provided by the Division of Nursing Research and Biostatistics Department at St. Jude Children's Research Hospital
Human Subjects: The risks to subject are minimal. Retinal irritation is unlikely; however, each patient will be issued glasses for eye protection. Patients will be informed of this during informed consent discussion. Adverse events will be monitored and reported and treated appropriately.

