## 6.3 Off-Study Evaluations

1. Patients are off-study on last day (Day +20 or engraftment or absence of mucositis)

of PBM administration except for patients undergoing autologous tandem transplant will discontinue treatment with mucositis resolution and then resume light therapy with second transplant. Thus, these patients will remain on study until resolution of mucositis after second transplant. Therefore, will not reconsent with the second transplant, parents and patient may refuse if desired

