## 10.2 Statistical Analyses

### 10.2.1 Statistical analysis for the primary objective

*To evaluate the feasibility and efficacy of photobiomodulation therapy (PBM) in reducing oral mucositis in children and adolescents at risk for grade 3 oral mucositis undergoing an allogeneic hematopoietic cell transplant (HCT).*

Hypothesis 1: Children and adolescents will receive 75% of the attempted PMB treatment and will be less likely to develop grade 3 oral mucositis from the 1st day of conditioning to day +20 of transplant or engraftment.

Descriptive statistics (counts, percentages, mean, median, standard deviation and interquartile range) and confidence interval will be calculated for the percentage of successful treatment administered, total days on the protocol, days treatment is received, cumulative dose and the number of treatments received at each site.

The count, percentage and confidence interval will be calculated for allogeneic HCT patients who receive PBM and develop Grade 3 mucositis. Whether the percentage of the prospective sample is significantly different from the historical rate is accessed by the monitoring rule in Section 10.1.

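### The exposure table counts days on protocol through engraftment without the Day +20 limit that ends allogeneic PBM, so late engrafters are credited with days on which no treatment was scheduled

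*Combined protocol and SAP*

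**What the plan says.** The table of PBM delivered in Section 4.1 has three footnotes.

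- Footnote a: "Days on protocol defined as from the first day of hematopoietic cell transplantation conditioning through engraftment".
- Footnote b: "Days received treatment defined as days with treatment during any of the on-protocol days". Treated days are thus counted only inside the footnote a interval.
- Footnote c defines cumulative dose as "single treatment dose multiplied by the number of treatment sites (up to 6 in total) for each treatment session", with no mention of on-protocol days.

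The treatment window is set elsewhere.

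- End, allogeneic: Section 4.1 says "those undergoing an allogeneic HCT will have treatment daily until engraftment or +Day 20 (event occurring first". Hypothesis 1 in Section 1.1 uses the same limits.
- Start: the Brief Outline of Treatment Plan in the overview has PBM "beginning on the first morning of the conditioning regimen (plus/minus 2 days". The Brief Overview and Section 4.1 give the first morning or first day of conditioning with no tolerance.
- Off study: Section 6.3 takes patients off study on the last day of PBM and lists Day +20 among the possible last days.
- Tandem autologous patients, also in Section 6.3: they "discontinue treatment with mucositis resolution and then resume light therapy with second transplant", under the same consent.

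The counts are planned outputs. Section 10.2.1 lists, for the primary objective, descriptive statistics on "total days on the protocol, days treatment is received, cumulative dose and the number of treatments received at each site". Section 10.2.3 repeats the list for patients with and without play-based preparation.

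**The concern.** Footnote a has no Day +20 limit. The efficacy window and the matched comparison, described directly after the table in Section 4.1, both stop at Day +20 or engraftment, so the footnote is out of line with its own section as well as with the PBM schedule.

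The consequence is a count that does not measure what its label suggests. For an allogeneic patient engrafting after Day +20, it includes days when no PBM was due and the patient had already left the study. The columns for days on protocol and days treated stand side by side and will be read together. A fully treated late engrafter would then look partly untreated, for a reason that has to do with engraftment and not with whether PBM could be delivered. At the other end, a session given before conditioning day 1 is real exposure that footnote b leaves out, although footnote c as worded could include it in the dose.

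**Working it through.** No figure in the plan depends on this definition, so there is nothing to reproduce. The check is a day count.

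**Can engraftment after Day +20 occur?** Section 2.2 (the institution's retrospective review) reports mucositis onset with median Day 3, range Day -3 to Day 9, and onset to engraftment with median 9 days, range 3 to 26.

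- The patient with the 26-day interval engrafted no earlier than -3 + 26 = Day +23 and no later than 9 + 26 = Day +35.
- Adding the medians, as a rough guide only, gives 3 + 9 = Day +12 for a typical patient.

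At least one reviewed patient therefore engrafted after Day +20, while the typical patient engrafted well before it.

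**Size of the mismatch at the end of the window.** Let conditioning start on Day -C and engraftment fall on Day +E, and include Day 0. The documents do not give C, so I assume 7 and show 5 and 10 as a range.

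- Days on protocol under footnote a = C + 1 + E
- Scheduled allogeneic PBM days under Section 4.1 = C + 1 + min(E, 20)

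For C = 7 and E = 23, these are 7 + 1 + 23 = 31 and 7 + 1 + 20 = 28. Treated days over on-protocol days for a patient who misses nothing:

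| Engraftment | C = 5 | C = 7 | C = 10 |
|---|---|---|---|
| Day +12 | 18/18 = 100% | 20/20 = 100% | 23/23 = 100% |
| Day +20 | 26/26 = 100% | 28/28 = 100% | 31/31 = 100% |
| Day +23 | 26/29 = 90% | 28/31 = 90% | 31/34 = 91% |
| Day +28 | 26/34 = 76% | 28/36 = 78% | 31/39 = 79% |
| Day +35 | 26/41 = 63% | 28/43 = 65% | 31/46 = 67% |

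With the count ended at engraftment or Day +20, every cell becomes 100%.

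**Sessions before the window.** A start 2 days early leaves 2 delivered days outside footnote b. With C = 7 this is 2/22 = 9% of delivered days for engraftment on Day +12, and 2/30 = 7% if treatment runs to Day +20. For engraftment on Day +12 the range is 2/20 = 10% (C = 5) to 2/25 = 8% (C = 10).

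**Second course.** Footnote a names one conditioning start and one engraftment. It does not say whether the count restarts for a tandem transplant or how the gap between courses is treated.

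**The case against.** The strongest reply is that no decision rests on this count. The feasibility criterion in Section 4.1 divides successful treatments by attempted treatments and requires more than 75%. Footnote a enters neither term, nor the efficacy endpoint or the sample size in Section 10.1. That stands in full. It also stands that the plan defines no ratio of treated to on-protocol days and no dose per day: the percentages above are what a reader would derive from adjacent columns.

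A second reply is that footnote a is loose shorthand, because Section 6.3 already puts patients off study at Day +20 and Section 6.2 calls the logged variable days on PBM protocol. That may well be the intention, but a programmer following the footnote literally would produce the longer count.

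A third reply is that counting from conditioning day 1 is sensible for late starters, since PBM was intended from then. I agree. A denominator beginning at the actual first session would hide late starts.

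Three stronger readings are tempting and go too far.

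- A reader might take 65% or so as the expected distortion. That needs the latest onset and the longest interval in one patient, which Section 2.2 does not show. Nor does it state that patient's transplant type, and the Section 4.1 Day +20 limit applies to allogeneic patients.
- A reader might infer that autologous sessions after engraftment are lost, or that a whole second tandem course is. The autologous stop rule joins engraftment and resolution with an unqualified or, one sentence of Section 4.1 points to resolution alone, and footnote a can be read as applying per transplant.
- A reader might infer that dose and days necessarily cover different periods. Footnote c allows this but does not say it.

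**Conclusion.** The definition is inconsistent with the allogeneic treatment window in Section 4.1 and the off-study rule in Section 6.3, and should be corrected. Taking the Section 4.1 stop rule as written and assuming 7 conditioning days, a fully treated allogeneic patient engrafting on Day +23 shows 28 of 31 days. Day +23 is the earliest day that the Section 2.2 ranges allow for the longest interval. The error increases with later engraftment and vanishes for engraftment by Day +20, probably the usual case. How many patients engraft later is not stated.

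The loss of sessions before conditioning day 1 follows directly from footnote b if the plus/minus 2 days applies. For tandem patients the finding is only that the count is undefined.

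The effect is confined to the descriptive exposure summaries in Sections 4.1, 10.2.1 and 10.2.3. The documents do not support a claim that the feasibility conclusion or the efficacy result would change.

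**What to change.** 1. For allogeneic patients, end footnote a at engraftment or Day +20, whichever is first, to match Sections 4.1 and 6.3. This also gives an end date for a patient who never engrafts.
2. For autologous patients, end it at the last scheduled PBM day, counted separately for each transplant course. The sponsor must first reconcile the stop wording in the Brief Overview, the Brief Outline of Treatment Plan and Section 4.1. The Brief Outline attaches the mucositis-based stop to allogeneic patients, where the other two attach it to autologous patients.
3. Count every delivered session in both days treated and cumulative dose, including any before conditioning day 1. Starting the count at the earlier of conditioning day 1 and the first session does this and keeps the days before a late start in the denominator. With C = 7 and treatment to Day +20, a start 2 days early gives 30 of 30 and a start 2 days late gives 26 of 28.
4. The sponsor should reconcile the start wording across the same three places. No treatment rule is proposed here.

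The cost is a revision of the footnotes and a sentence in Section 10.2. The Section 6.2 treatment log already collects days treated and dose, and chart abstraction collects time to engraftment.
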